7.1.2 Secondary Effectiveness Endpoint

The secondary effectiveness endpoint is the difference between the proportions ($\pi_{\text{test}} - \pi_{\text{control}}$) with an improvement at Month 6 in blinded evaluator's GAIS on the side treated with Radiesse (π_{test}) and on the side treated with Restylane (π_{control}).

The hypothesis on the secondary effectiveness endpoint and the corresponding analysis will be similar to that specified for the primary effectiveness analysis, however, using a less conservative margin of $\Delta = 0.15$ (or 15%). This analysis will be of exploratory nature without any inferential considerations.

7.1.3

[REDACTED]

7.2 Safety Endpoints

All safety analyses will be performed on the SES.

The assessment of safety will be based mainly on the frequency of adverse events.

Only treatment-emergent AEs (TEAEs) will be analyzed, which are defined as AEs with onset or worsening after the first administration of Restylane or Radiesse.

TEAEs will be summarized for each treatment group (as applicable) by the incidence of at least one event, the number of events, and the incidence using Medical Dictionary for Regulatory Activities (MedDRA) version xxx preferred terms within the system organ classes (SOCs). The detailed information on AE including the outcome will be listed.

In case of missing intensity or missing causal relationship of an AE the worst case principle will be applied, i.e. a missing intensity will be set to “severe” and a missing causal relationship will be set to “related”.

7.2.1 Primary Safety Endpoint(s)

Not applicable.

7.2.2 Secondary Safety Endpoints

Not applicable.

7.2.3 Other Safety Endpoints

7.2.3.1 All AEs

AEs will be summarized overall, by worst intensity and by worst causal relationship, each by SOC and PT. In addition, the frequency of subjects with TEAEs are provided by PT only. The number and percentage of subjects with at least one non-serious TEAE with incidence $\geq 5\%$ will be displayed by SOC and PT.

7.2.3.2 Serious Adverse Events (SAEs)

Serious TEAEs will be summarized by SOC and PT.

7.2.3.3 Related Adverse Events

An AE is considered to be “related” to study treatment if “relationship to study device” or “relationship to procedure” is ticked as “yes” or is missing (i.e., the relationship cannot be ruled out). Related TEAEs will be summarized by SOC and PT.

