5.1 Study Endpoints

5.1.1 Primary Effectiveness Endpoint:

Compare the proportion of NLFs with treatment success in the Radiesse and Restylane groups at Month 6. Treatment success is defined as $a \ge 1$ -point improvement from baseline, as assessed by a blinded evaluator on a 5-point Wrinkle Severity Rating Scale (WSRS) scale⁷.

5.1.2 Secondary Effectiveness Endpoint:

Compare the proportion of NLFs with an "improvement" in the blinded evaluator's Global Aesthetic Improvement Scale (GAIS) score at Month 6 between the NLFs treated with Radiesse versus Restylane. An "improvement" on the GAIS will be classified as "improved", "much improved", or "very much improved". The pre-treatment photograph will be used as a reference to assess the level of improvement at Month 6.

5.1.4 Safety Endpoints:

• Incidence of adverse events (AEs) including serious adverse events (SAEs), AEs related to treatment as assessed by the investigator, and AEs leading to discontinuation during the study.

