10 SAFETY ASSESSMENTS

10.1 **AEs**

The general definition for an adverse event (AE) is an untoward medical occurrence which does not necessarily have a causal relationship to the study product. An AE can therefore be any unfavorable, unintended, or untoward clinical sign (including an abnormal laboratory finding), unintended disease or injury, a symptom or disease temporally associated with the use of the study product, whether or not considered related to that device. An AE may also apply to other users or persons as noted in Note 3 below.

- NOTE 1: This includes events related to the study product(s).
- NOTE 2: This includes events related to the procedures involved (any procedure in the clinical study protocol).
- NOTE 3: For users or other persons this is restricted to events related to the study product(s).

AEs may include, but are not limited to, subjective or objective symptoms spontaneously offered by the subject, uncovered by review of concomitant medications or therapies, and/or observed by the investigation site staff. The investigator will determine the description (sign, symptom, or diagnosis), onset, resolution, seriousness, severity, cause and action taken for any event.

Disease signs and symptoms that existed prior to ICF sign off are not considered AEs. Recurring symptoms associated with pre-existing conditions are not considered AEs unless they have a clinically significant increase in severity and/or frequency.

Elective treatments planned before screening and which are documented in the subject's source data are usually not regarded as AEs. However, elected procedures should be postponed, if possible, until the subject completes their participation in the investigation. All adverse events will be collected on each subject until to the 12-month follow-up visit. The subject's course must be monitored until the event has subsided or, in a case of permanent impairment, until the event stabilizes and the overall clinical outcome has been ascertained.

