10.1.2 Definition of Causal Relationship

An AE is considered to be "related" to IP(s) if a causal relationship between the IP(s) and an AE is at least a reasonable possibility (i.e., the relationship cannot be ruled out). In this case, the event is considered an ADE. If the event is serious (see below), it is a serious adverse device effect (SADE).

The expression "reasonable causal relationship" is meant to convey that there are facts (evidence) or arguments to suggest a causal relationship (International Conference on Harmonization (ICH) E2A guideline). Otherwise, the relationship should be considered as "not related."

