10.2 Adverse Device Effect (ADE)

An ADE is defined as an AE related to the use of a study product.

NOTE 1: This includes any AE resulting from insufficiencies or inadequacies in the IFU, the deployment, the implantation, the installation, the operation, or any malfunction of the study product(s).

NOTE 2: This definition also includes any AE that is a result of a use error or intentional misuse.

10.3 **Device Deficiency**

A device deficiency is defined as an inadequacy of a medical device related to its identity, quality, durability, reliability, safety or performance, such as malfunction, misuse or use error and inadequate labeling.

Note: A device deficiency that may cause SAE and have led to an SADE (for definition see Section 10.5) is to be reported in the same way as an SAE.

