10.6.1 Handling and reporting of adverse event (AE) and device deficiency

Subjects will be carefully monitored during the clinical investigation for possible AEs.

All AEs or reactions must be reported in subject's medical records (source documents) and in the eCRF.

In addition, the investigator and staff shall also carefully report any device deficiencies. Any AEs and device deficiencies observed will be fully investigated, documented and followed up until the event is either resolved or adequately explained.

In cases of surgical or diagnostic procedures, the condition/illness leading to such a procedure is considered as the AE rather than the procedure itself.

In case of a fatality, the cause of death is considered as the AE, and the death is considered as its outcome. In this case, the primary cause of death (the event leading to death) should be recorded and reported as an SAE. "Death" will be recorded as the outcome of this respective event; death will not be recorded as a separate event. Only if no cause of death can be reported (e.g., sudden death, unexplained death), the death per se might be reported as an SAE.

Pre-existing conditions that do not worsen during the course of the clinical investigation are not reportable as AEs. To determine whether a condition has worsened, it is compared to the condition of the subject at screening.

Data pertaining to AEs will be collected during each investigation visit based on the subject's spontaneous description, through investigator inquiry, or discovered in the course of examinations done during the visit. The investigator will assess and record any AE in detail in the subject file and on the eCRF AE report form. The following information must be recorded:

- AE diagnosis or main symptom.
- Location of AE: systemic or restricted to injection area. In case of local reaction, the corresponding area should be reported.
- Date of onset.
- Time of onset (if known).
- Date of worsening.
- Time of worsening (if known).
- Severity (maximum observed; see Section 10.1.1).

- Causal relationship (see Section 10.1.2).
- Serious (yes or no).
- Outcome (see Section 10.1.3).
- Action taken with study product(s).
- AE leading to discontinuation of the investigation (yes or no).
- Stop date (and time if known).

After completion of all scheduled visit assessments, the investigator must document any AEs arising from these assessments.

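### The SAP counts procedure-related events as related to study treatment, wider than the protocol's product-only definition, and no readable output requires the device-related incidence on its own

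*SAP*

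**What the plan says.** Protocol section 5.1 names, among the safety endpoints, "AEs related to treatment as assessed by the investigator". Protocol section 12.3.2 and SAP section 6.2 repeat that wording.

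Protocol section 10.1.2 gives the only definition of related in the protocol. An event qualifies "if a causal relationship between the IP(s) and an AE is at least a reasonable possibility", and it is then an ADE. The list of items to record in protocol section 10.6.1 has one causality entry, which points to that definition: "Causal relationship (see Section 10.1.2". Protocol section 10.2 adds "An ADE is defined as an AE related to the use of a study product", and its first note extends this to events resulting from inadequacies in, among other things, "the deployment, the implantation, the installation, the operation, or any malfunction of the study product(s".

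SAP section 7.2.3.3 uses two fields. An event is related to study treatment if "relationship to study device” or “relationship to procedure” is ticked as “yes” or is missing". One summary by system organ class (SOC) and preferred term (PT) follows. SAP section 7.2 also says that "a missing causal relationship will be set to “related".

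**The concern.** The protocol's definition has no procedure limb. The SAP adds one, and the readable text of its section on changes (section 8, partly redacted) does not mention it. ADE and SADE stand in the SAP's abbreviation list, but no readable section tabulates either.

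This is a pre-market device study, so the natural reading of a related-event rate per filler is the rate of events possibly due to that filler. A rate that also takes in events the investigator attributed only to a procedure answers a broader question. If it is the only related-event table, the reader of the report cannot recover the quantity the protocol defines.

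**Working it through.** There is no figure in the plan to reproduce; the check is a comparison of texts, followed by an illustration.

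**Step 1. How each rule classifies an event.**

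| Device field | Procedure field | Protocol 10.1.2 | SAP 7.2.3.3 as written |
|---|---|---|---|
| yes | any | related | related |
| no | yes | not related, unless section 10.2 makes it a device effect | related |
| no | missing | not related | related |
| missing | any | no rule given | related |
| no | no | not related | not related |

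The rules part company in the second and third rows. In the third, a blank procedure field outweighs an explicit no for the device. That is an imputation, whereas the endpoint is worded as the investigator's assessment.

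**Step 2. Which procedures could be involved.** The first note in protocol section 10.1 brings in product-related events. The second reads: "This includes events related to the procedures involved (any procedure in the clinical study protocol". If the procedure field has the same scope, it reaches beyond the injection. Blood is taken at Visits 1, 2, 5 and 7 (protocol sections 9.1.2.3 and 9.2.3). SAP section 7.2 analyses only events with onset or worsening after the first administration. Visit 1 laboratory tests precede treatment, and the baseline pregnancy result must be available before injection. So only the draws at Visit 5 (Month 6) and Visit 7 (Month 12) can realistically yield such an event. A venepuncture bruise there, marked device no and procedure yes, would be reported as related to study treatment.

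**Step 3. What pooling can do to a comparison of the fillers.** Assume, for illustration only, device-related events on 20% of Radiesse folds and 10% of Restylane folds: difference 10 points, ratio 2.0. Let d be the device-related rate and q the procedure-related rate on a side, independent of each other. The pooled rate is 1 - (1 - d)(1 - q).

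| q Radiesse / Restylane | Pooled Radiesse | Pooled Restylane | Difference (points) | Ratio |
|---|---|---|---|---|
| 10% / 10% | 1 - 0.8×0.9 = 28% | 1 - 0.9×0.9 = 19% | 9 | 1.47 |
| 30% / 30% | 1 - 0.8×0.7 = 44% | 1 - 0.9×0.7 = 37% | 7 | 1.19 |
| 60% / 60% | 1 - 0.8×0.4 = 68% | 1 - 0.9×0.4 = 64% | 4 | 1.06 |
| 80% / 80% | 1 - 0.8×0.2 = 84% | 1 - 0.9×0.2 = 82% | 2 | 1.02 |
| 40% / 20% | 1 - 0.8×0.6 = 52% | 1 - 0.9×0.8 = 28% | 24 | 1.86 |
| 20% / 40% | 1 - 0.8×0.8 = 36% | 1 - 0.9×0.6 = 46% | -10 | 0.78 |

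Equal procedure rates dilute the difference. Unequal ones can widen it in absolute terms or reverse it. Unequal rates are plausible, because Radiesse is injected below the dermis with a 27 G needle and Restylane into the mid dermis with a 30 G needle.

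**The case against.** The strongest reply is that the endpoint speaks of treatment, and treatment here is an injection. Counting procedure-related events is then a fair reading, and one that errs towards reporting more harm. Section 10.2 of the protocol already brings deployment, implantation and use error into the ADE definition, so many injection reactions would be device effects anyway. The safety analysis is descriptive and no test between fillers is stated. Summaries are per treatment group where applicable and by preferred term, and the location of local reactions is recorded, so an arm bruise need not be charged to either filler. The eCRF, the mock shells and the content of SAP Appendix 1 are not available. The procedure field may mean the injection only, a device-only table may exist, and the planned summary by worst causal relationship does not say which field it uses.

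Much of this stands. A reader might infer that the SAP reports a different endpoint from the protocol's. The documents do not support that, because both use the same endpoint wording and section 10.2 blurs the line between device and injection. A reader might also infer that the rule masks differences between the fillers. That needs common and similar procedure rates on both sides, which no document gives.

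What remains is that section 10.1.2 is the protocol's only definition of related, that the SAP departs from it without a readable explanation, and that the readable SAP does not require the narrower table. Section 10.2 ties its extensions to the study product and does not reach a blood draw.

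**Conclusion.** The concern holds as a mismatch of definitions with a gap in the outputs. An event the investigator marked as unrelated to the device can be reported as treatment-related, and the pooled rate does not isolate the device effect. The direction and size of any distortion between fillers are unknown; the span of 24 to -10 points around a 10-point difference shows only what assumed, independent rates could produce. The venepuncture example depends on the procedure field covering any protocol procedure, which the documents do not establish. The finding about outputs is limited to the readable text. The primary effectiveness conclusion is untouched, so this is a correction to make before lock and not a threat to the study.

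**What to change.** 1. Reconcile SAP section 7.2.3.3 with protocol sections 10.1.2 and 10.2, or list the wider rule in SAP section 8 with its reason. Check against the current protocol: the SAP cites version 1.2, and the protocol supplied is version 1.3.
2. State in the SAP that injection, deployment and implantation reactions covered by protocol section 10.2 count as device-related, so that a device table does not lose them.
3. Tabulate two sets of treatment-emergent events separately by filler, SOC and PT: device-related (device yes or missing) and procedure-only. Keep the pooled device-or-procedure table beside them, so that the most inclusive rate is still reported.
4. Identify events from procedures other than the injection by the recorded event location or at the blind data review. The documents show no dedicated field for this.

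The device-related table uses a field the SAP already names. The cost is a wording change, some review effort for step 4, and one or two extra tables.

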7.2.3.4 AEs Leading to Discontinuation

AEs leading to discontinuation are AEs that are recorded as leading to study termination in electronic Case Report Form (eCRF), and will be summarized by SOC and PT.

7.2.3.5 Vital signs

Vital signs will be analyzed using descriptive summary statistics including the number of non-missing observations, mean and standard deviation, median, upper and lower quartiles, minimum and maximum for values and changes from baseline.

7.2.3.6 *Clinical Laboratory Assessments*

Variables from laboratory assessment with continuous outcomes will be analyzed using descriptive summary statistics including the number of non-missing observations, mean and standard deviation, median, upper and lower quartiles, minimum and maximum for values and changes from baseline. Categorical data (e.g. clinical significance) will be analyzed using shift tables.

7.3 [REDACTED]

[REDACTED]

7.3.1 *Disposition and Withdrawals*

The assignment of subjects to analysis populations, completion of study/ premature termination of study and protocol deviations/other reasons for exclusion from analysis sets will be summarized in frequency tables. Detailed information will be provided in listings.

7.3.2 *Demographic and Other Baseline characteristics*

Demographic data and other baseline characteristics will be summarized for the SES, FAS and PPS. If the 'randomized subjects set' is not equal to the SES, demographic data and other baseline characteristics will be summarized for the 'randomized subjects set', too. Continuous data will be analyzed using descriptive summary statistics (n, mean, standard deviation, median, lower and upper quartiles, minimum and maximum). Categorical data will be analyzed using frequency tables. No homogeneity tests will be performed.

The following demographic data will be summarized for this study: sex, age (calculated relatively to consent date), age category, ethnicity, race, Fitzpatrick skin type, height, weight and Body Mass Index (BMI).

Detailed information will be provided in listings.

7.3.3 *Medical History*

Medical history and concomitant diseases will be summarized based on MedDRA system organ class and preferred term levels for the SES.

7.3.4 *Prior/Concomitant Medications/Treatments*

Prior and concomitant medications/treatments will be listed and summarized by Anatomical Therapeutic Chemical (ATC) class and World Health Organization Drug Dictionary (WHODD) generic name. Frequencies of concomitant medications/treatments will be given

CONFIDENTIAL

Template: tem-sap-v4.0-20151126

File name:Merz RADIESSE SAP V1.0 20180917.docx

based on different ATC code levels as well as by generic name for the SES. Study Product Exposure

The injected volumes of Radiesse and Restylane at the baseline visit and the 4-week/Month 1 optional touch-up visit, as well as the total volume administered will be summarized, using mean, standard deviation, median, minimum and maximum based on SES.

7.4 Special Statistical/Analytical Issues

7.4.1 Discontinuations and Missing Data

Effectiveness:

Besides the analyses based on observed data, additional sensitivity analyses for primary and secondary effectiveness endpoints will be carried out with missing data imputed using single value imputation methods. Imputations will be performed until Month 6.

Missing effectiveness data will be imputed as follows:

Worst Case Scenario (WCS):

- For the WCS method, missing post-baseline data for Radiesse treatment group will be imputed as non-responders, while missing post-baseline data for Restylane treatment group will be imputed as responders. As a result, the WCS is considered a conservative imputation method because missing values from the control are imputed as responders while missing values from the treatment are imputed as non-responders. The WCS will be used for sensitivity analysis. As this method is an extreme conservative method, an additional, probably more realistic but still conservative imputation method will be performed based on pattern (reason) of missingness:
- *Pattern Based Scenario (PBS):* At the BDRM, the reasons for subjects' withdrawals before Month 1, Month 3 or Month 6 assessment of the WSRS and/or GAIS assessment (with the consequence that these values are missing) are reviewed and assessed as "probably missing at random" or as "definitely or possibly missing not at random". Hereby "Lost to follow-up" will be assessed as "probably missing at random", while "AE related to treatment" will be assessed as "definitely or possibly missing not at random". For subjects with an assessment of "probably missing at random", no imputation will be performed. For subjects with an assessment of "definitely or possibly missing not at random", it will be checked whether the withdrawal is related to only one of the two treatments (this is the case if e.g. the AE leading to WD is located on one face side only). If so, the subject is treated as "non-responder" for this treatment and as "responder" for the other. If not, the subject is treated as "non-responder" for both treatments.

Safety:

Each medication/therapy will be allocated unambiguously either to previous medications or to concomitant medications.

- If stop date is before start of treatment: Previous medication
- If the stop date is at or after start of treatment or ongoing is checked: Concomitant medication
- Otherwise, if the stop date is missing or partially given:
 - Partial stop date available: Previous therapy if the latest possible stop date is before start of treatment; Concomitant therapy if the latest possible stop date is at or after start of treatment
 - If the stop date is completely missing: Concomitant therapy

Each finding on the medical history page will be allocated unambiguously either to medical history or to concomitant diseases.

- If the stop date is before start of treatment: Medical history
- If the stop date is at or after start of treatment or ongoing (even if it refers to a cut-off point before start of treatment) is ticked: Concomitant disease
- Otherwise, if the stop date is missing or partially given:
 - Partial stop date available: Medical history if the latest possible stop date is before start of treatment; Concomitant disease if the latest possible stop date is at or after start of treatment
 - Stop date is completely missing for findings coded as “Surgical and medical procedures”: Medical history
 - Stop date is completely missing for other findings: Concomitant disease

For AEs, imputation of missing start or stop dates will follow the steps below:

[figure not shown]
- If the start date (and time, if applicable) is partially missing but implies start before start of treatment or after date of final examination, the AE will be considered as Non-Treatment Emergent Adverse Event (TEAE).
- If the start date (and time, if applicable) is partially missing and possibly after start of treatment and before or after date of final examination, will be considered as TEAE.

AEs with completely missing onset dates will be considered treatment emergent; no estimation of the dates will be performed.

For the imputed analysis start date of adverse events (variable ASTDT) in the ADaM domain ADAE the following imputation rules related to any treatment period will be used if applicable:

Figure 1: Possible start/end dates of AEs

1. Available start and end information clearly indicates that the AE started and/or ended before first injection -> non treatment emergent

2. Available start and end information does not clarify whether the AE started before first injection or at any timepoint thereafter
-> imputed start = date of first injection -> TEAE for cycle 1

3. Available start and end information indicates that AE started after first injection -> imputed start = first possible date after first injection
-> TEAE for preceding injection

1a) If the start date is missing completely and the end date and time* does imply end before first injection then no imputation of start date and time will be performed.

1b) If the start date is partially missing and the partially missing start date and/or the end date and time* do imply start and/or end before first injection then set missing start day to 1 / missing start month to 1, if applicable and set start time (if not available) to 23:59, if not after end date/time (else set start time to end time) (e.g. start date of AE: 2008-11 end date of AE: 2009-02-01, end time 22:00 and first injection: 2008-12-06 T17:35 → imputed start date: 2008-11-01, start time: 23:59). Set imputation flags accordingly.

2a) If the start date is missing completely and end date and time* do not imply end before first injection then set imputed start date to date of first injection and set start time (if not available) to 23:59, if not after end date/time (else set start time to end time). (e.g. start date of AE: missing, end date of AE: 2008-12-31, end time 23:00, first injection date: 2008-12-06T17:35 → imputed start date: 2008-12-06, start time: 23:59). Set imputation flags accordingly.

2b) If the start date is partially missing and the non-missing part is the same as in first injection date and the end date and time* do not imply end before first injection, then set the imputed start date to the first injection date and set start time (if not available) to 23:59, if not after end date/time (else set start time to end time) (e.g. start date of AE: 2008-12, end date of AE: 2008-12-31, end time 23:00, first injection date: 2008-12-06T17:35 → imputed start date: 2008-12-06, start time: 23:59). Set imputation flags accordingly.

3) If the start date is partially missing and imputation rule 1b and 2b do not fit, then set missing day to 1 / missing month to 1, if applicable and set start time (if not available) to 23:59, if not after end date/time (else set start time to end time) (e.g. start date of AE: 2009-02 end date of AE: 2009-02-01, end time 22:00 and first injection: 2008-12-06 T17:35 → imputed start date: 2009-02-01, start time: 22:00). Set imputation flags accordingly.

End date or end time will not be imputed.

* The end date and time may be available completely, partly or may be missing.

7.4.2 *Interim Analyses*

In the mock shells it is specified for each table/listing whether it is to be produced for the interim report and/or amendment.

Statistical analyses will be performed when all subjects reach the 6 Month post initial injection time point. Primary effectiveness variable, secondary effectiveness variables and AE data will be analyzed using the snapshot of data for the first 6 months. A Statistical and a Clinical Study Report will be generated for the aforementioned analysis. They will be amended by a description and discussion of the analyses performed when all subjects have completed the study. For further details on which tables are produced for the Clinical Study Report and which for the amendment, please refer to the TFLs.

No examination for early termination is planned.

7.4.3 *Data Monitoring Committee*

There will be no data monitoring committee for this study.

7.4.4 *Multiple Comparisons/Multiplicity*

Only the analysis of the primary effectiveness endpoint based on PPS using observed values is of confirmatory nature. Further analyses on the primary effectiveness endpoint are performed for sensitivity reasons. Analyses of all other endpoints/variables is of exploratory nature.

7.4.5 *Examination of Subgroups*

No subgroup examination will be performed for this study.

